4.3.3. Sensitivity Analysis

Five sensitivity analyses of the primary efficacy endpoint of change in 28-day frequency of the primary seizure types will be performed:

1. Intermittent (random/sporadic) missing data during the DB phase and any missing data during the baseline phase will be assumed missing completely at random and the collected data will be used to calculate the 28-day seizure frequencies. For early drug termination prior to the end of the DB phase, caregivers will be instructed to continue to provide daily seizure records until the end of the 16-week DB phase (hence further preventing missingness).

In the first sensitivity analysis, the following imputation approach will be used for the primary outcome measure when a subject stops recording measurements permanently prior to the end of the DB phase: for those missing days, the corresponding median PBO data will be imputed (irrespective of treatment arm) as follows:

- Partition the subjects in the PBO arm into quartiles, where the quartile equals Floor [Rank*4/(n+1)], where Floor [.] is the integer floor function, Rank is the rank of the 28- day seizure frequency in the PBO arm based on all available PBO measurements during the 4-week baseline phase (tied scores receive tied ranks), and n is the number of subjects in the PBO arm.
- Assign each subject for whom imputation is needed into the quartile that covers the 28-day seizure frequency based on that subject's available measurements during the 4-week baseline phase. If a frequency is lower than the lower bound of the lowest quartile (which could happen only in the GNX arm), then assign that subject to the lowest frequency quartile; likewise, if a frequency is higher than the upper bound of the highest quartile, then assign that subject to the highest frequency quartile. If a frequency falls between two quartiles (which, again, could happen only in the GNX arm), then based on the distances between the frequency and the upper and lower bounds of the lower and higher quartiles, respectively, assign the subject to the closer quartile (in case of a tie, assign to the lower quartile).
- Within each quartile, compute the median 28-day seizure frequency in the PBO arm based on all available PBO measurements during the DB treatment phase. Label that 'X' and define 'A' to be 'X'/28, (i.e., the daily average on placebo during the DB phase).
- For any days (whether they be on the PBO or GNX arm) with missing counts due to a subject stopping recording measurements permanently, impute 'A' from the corresponding quartile on that day.
- 2. The second sensitivity analysis will explore the possibility that subjects who stop recording their seizure counts tend to have higher seizure counts than the other subjects. The imputation method described in the 3rd and 4th bullets above, except that quartiles are not used, will be modified to use the median of the 5 highest counts (equivalent to the 3rd highest count) among all the PBO subjects with data.
- 3. The third sensitivity analysis will be performed on subjects who achieved their maintenance dose at the start of the maintenance period. This analysis will exclude those subjects who are still titrated continuously during maintenance period.
- 4. The fourth sensitivity analysis will be performed for the primary outcome measure by excluding all intercurrent events.

4.3.4. Key Secondary Efficacy Endpoints

Hypothesis testing will be performed for the three key secondary endpoints:

1. Percentage change from baseline in 28-day primary endpoint seizure frequency during the maintenance period.

The hypothesis testing is:

$$H_0$$
: $\theta_{PBO} = \theta_{GNX}$ H_a : $\theta_{PBO} \neq \theta_{GNX}$

where θ_{GNX} is the percentage change of seizure frequency during the maintenance period relative to the baseline for participants who treated with GNX and θ_{PBO} is similarly defined for participants receiving placebo.

Similar to the primary efficacy endpoint, the test will be performed using the Wilcoxon Rank-Sum statistic using a 2-sided significance level of 0.05.

2. Number (%) of participants considered treatment responders during the DB phase. The hypothesis testing is:

$$H_0: \gamma_{PBO} = \gamma_{GNX} \quad vs. \quad H_a: \gamma_{PBO} \neq \gamma_{GNX}$$

where γ_{GNX} is the proportion of participants who treated with GNX experiencing $\geq 50\%$ reduction from baseline in 28-day seizure frequency based on the primary seizure types and γ_{PBO} is similarly defined for participants receiving placebo.

The test comparison will be analyzed using Fisher's Exact test and the corresponding p-value will be provided. The difference in proportions along with the 95% confidence interval for the difference also will be presented. The number and percentage of subjects experiencing a reduction (improvement) of at least 50% from baseline in the 28-day seizure frequency of the primary seizure types will be summarized. In addition, a cumulative responder curve figure will be provided, in which the X-axis represents amount of improvement in increments of 5%, and the Y-axis represents the percentage of subjects improving by at least the amount on the X-axis. The treatment groups will be presented separately within the figure.

3. Number (%) of participants considered treatment responders during the maintenance phase.

This is similar to #2 above. The only difference will be replacing the DB phase by the maintenance phase.

4. CGI-I at the last scheduled visit in the DB phase.

The hypothesis testing is:

$$H_0$$
: $OR_{GNX/PBO} = 1$ vs. H_a : $OR_{GNX/PBO} \neq 1$

where $OR_{GNX/PBO}$ is the odd ratio between GNX and PBO in regard to CGI-I.

The CGI-I is 7-point scale, and the number and percentage of subjects with each score will be summarized. The scores range from 1=very much improved and 7=very much worse. The CGI-I is completed by both parent/caregiver/LAR and clinician. The score at the last visit in the DB treatment phase will be analyzed using ordinal logistic regression. Proportional odds modelling will be carried out by including treatment group as a factor. The estimated odds ratios (GNX vs. PBO), 95% CI for the odds ratios, and the p-value testing the null hypothesis that the odds ratio is equal to 1, will be presented.

4.3.5. Secondary Efficacy Endpoints

Summary statistics including confidence intervals for the treatment differences will be used to summarize the results for the secondary endpoints. Testing, as outlined below, will be used for the secondary endpoints.

Change from baseline in ADAMS total score and sub-score.

The ADAMS (Anxiety, Depression, and Mood Scale) is a rating scale designed to screen for anxiety and depression in individuals with intellectual disability. The 28-question scale is filled out by the parent/caregiver/LAR and is based on the subject's behavior during the past 6 months at the Baseline visit and since the last visit at the subsequent visits. Each of the questions are scored as 0 = Not a problem, 1 = Mild problem, 2 = Moderate problem, or 3 = Severe problem. The questions are grouped into 5 subscales:

Manic/ Hyperactive Behavior	Depressed Mood	Social Avoidance	General Anxiety	Obsessive/ Compulsive Behavior
3.	5.	2.	1.	8.
4.	9.	6.	3.	16.
12.	10.	13.	7.	20.
17.	14.	19.	11.	
22.	18.	21.	15.	
	23.	25.	24.	
	28.	27.	26.	

The subscale totals will be summarized with descriptive statistics of the baseline and post-baseline values and the arithmetic changes from baseline.

Change from baseline in quality-of-life scales: Peds-QL-FIM, SF-36, and ELDQOL.

Peds-QL-FIM

The Peds-QL-FIM is designed to measure the impact of pediatric chronic health conditions on parents and the family. The Peds-QL-FIM measures parent self-reported physical, emotional, social, and cognitive functioning, communication, and worry. The module also measures parent reported family daily activities and family relationships (see Protocol Section 10.14).

Total Score is computed by averaging all 36 items. Parent HRQOL Summary Score is computed by averaging 20 items in Physical, Emotional, Social, and Cognitive Functioning. Family Summary Score is computed by averaging 8 items in Daily Activities and Family Relationships.

SF-36

The SF-36 is a multi-purpose survey designed to capture participant or parent/caregiver perceptions of own health and well-being. The SF-36 has 36 items grouped in 8 dimensions: physical functioning, physical and emotional limitations, vitality, social functioning, bodily pain, general, and mental health (see Protocol Section 10.15).

Scoring the 36-Item Health Survey is a two-step process. First, precoded numeric values are recoded per the scoring key given in Table 1. Note that all items are scored so that a high score defines a more favorable health state. In addition, each item is scored on a 0 to 100 range so that the lowest and highest possible scores are 0 and 100, respectively. Scores represent the percentage of total possible score achieved. In step 2, items in the same scale are averaged together to create the 8 scale scores. Table 2 lists the items averaged together to create each scale. Items that are left blank (missing data) are not taken into account when calculating the scale scores. Hence, scale scores represent the average for all items in the scale that the respondent answered.

Table 1: Recoding Items for SF-36

Item numbers	Change original	To recoded
	response category	value of:
1, 2, 20, 22, 34, 36	1 →	100
	2 ->	75
	3 →	50
	4 →	25
	5 →	0
3, 4, 5, 6, 7, 8, 9, 10, 11, 12	1 →	0
	$2 \rightarrow$	50
	3 →	100
13, 14, 15, 16, 17, 18, 19	1 ->	0
	$2 \rightarrow$	100
21, 23, 26, 27, 30	1 →	100
	2 ->	80
	3 →	60
	4 →	40
	5 →	20
	6 →	0
24, 25, 28, 29, 31	1 →	0
	2 ->	20
	3 →	40
	4 →	60
	5 →	80
	6 →	100

Item numbers	Change original response category	To recoded value of:
32, 33, 35	1 →	0
	$2 \rightarrow$	25
	3 →	50
	4 →	75
	5 →	100

Table 2: Averaging Items to Form Scales for SF-36

Scale	Number of items	After recoding per Table 1, average the following items
Physical functioning	10	3 4 5 6 7 8 9 10 11 12
Role limitations due to physical health	4	13 14 15 16
Role limitations due to emotional problems	3	17 18 19
Energy/fatigue	4	23 27 29 31
Emotional well-being	5	24 25 26 28 30
Social functioning	2	20 32
Pain	2	21 22
General health	5	1 33 34 35 36

ELDQOL

The ELDQOL is a 70-item parent/caregiver-reported measure that examines seizure severity, seizure related injury, AED side effects, behavior, mood, physical status, cognitive and social functioning, communication, overall health and quality of life, and family concerns. The higher the score, the poorer the participant's quality of life (see Protocol Section 10.16). See the scoring instructions below:

Scoring instructions for 4 subscales of the re-validated version of ELDQOL

Seizure Severity Scale (Qs. 1 – 14)

Qs. 1, 5, 7, 8, 9, 10, 11, 13

Reverse the individual item scoring so that

- 1 = 4
- 2 = 3
- 3 = 2
- 4 = 1
- 5 define as a missing value so that it is not included in the calculation of the scale score

Qs. 4, 12

Reverse the individual item scoring so that

- 1 = 4
- 2 = 3
- 3 = 2
- 4 = 1
- 5 = 0
- 6 define as a missing value

Qs. 2, 14

5 - Define 5 as a missing value. Other scores unchanged.

Qs. 3, 6

5 = 0

Define 6 as a missing value.

Other scores unchanged

Total scale score range = 10-56

Side-effects Profile (Qs. 17 & 18) (Only items in Q.18 used to compute sub-scale.)

Score is the sum of the individual scores for each of the 19 items in Q.18

For each item, score of 5 - define as a missing value.

Any additional problems itemised by respondents should be recorded, but are not added to the total scale score.

Total scale score range = 19-76, where high scores = high level of side effects reported.

Behaviour (Qs. 19 - 27)

Qs.19, 24, 25, 26

Define 5 as a missing value Other scores unchanged

Qs. 20, 21, 27

Reverse scoring so that:

1 = 4

2 = 3

3 = 2

4 = 1

5 - define as a missing value

Qs.22, 23

Recode so that:

5 = 4

6 – define as a missing value Other scores unchanged

Total scale score range = 9-36

Mood Scale (Q. 28)

Reverse scoring of negative items (aggressive, irritable, tearful, hyperactive, sad, agitated, restless, tantrum-prone, frustrated, withdrawn), so that:

1 = 4

2 = 3

3 = 2

4 = 1

5 - define as a missing value

Total Scale score range = 16-64

General points

For each subscale, higher score = poorer QOL / functioning.

Give non-responses a missing value (suggest 9 or -9).

The mean score for each subscale is computed as the sum of the items divided by the number of items answered. To take account of any missing data in a subscale, the mean of the completed items can be imputed, providing at least 50% of the items are completed. If more than 50% of the items in the subscale are missing, then the total subscale score should be classed as a missing value.

All scales and subscales will be summarized separately with descriptive statistics of the baseline and post-baseline values and the arithmetic changes from baseline.

Change from baseline in the percentage of seizure-free days during the DB phase, based on primary endpoint seizure type.

The percentages of seizure-free days will be based on the primary seizure types. Post-baseline percentage of seizure-free days will be calculated as the number of days in the DB treatment phase with zero seizures divided by the number of days with seizure data in the phase, multiplied by 100. The baseline percentage of seizure-free days will be calculated as the number of days in the 4-week baseline phase with zero seizures divided by the number of days with seizure data in the baseline phase, multiplied by 100.

The baseline and post-baseline values and the arithmetic changes from baseline will be summarized using descriptive statistics.

CGI-CSID at the last scheduled visit in the DB phase.

The CGI-CSID is from the 7-point Caregiver Global Impression of Change in Seizure Intensity/Duration instrument. The scores range from 1=very much improved and 7=very much worse. The number and percentage of subjects with each score will be summarized.

Participants with a $\geq 25\%$ and $\geq 75\%$ reduction from baseline in primary endpoint seizure frequency during the DB phase.

Number (%) of subjects considered treatment responders, defined as those with a \geq 25% and \geq 75% reduction from baseline in primary seizure frequency during the DB phase will be summarized.

Participants with a $\geq 25\%$, $\geq 50\%$, and $\geq 75\%$ reduction from baseline in primary endpoint seizure frequency during the maintenance period.

Number (%) of subjects considered treatment responders, defined as those with a \geq 25%, \geq 50%, and \geq 75% reduction from baseline in primary seizure frequency during the maintenance period will be summarized.

Responder analysis for primary endpoint seizures and all seizures during the double-blind phase using the following response categories: $\leq 0\%$, > 0% to < 25%, $\geq 25\%$ to < 50%, $\geq 50\%$ to < 75%, and $\geq 75\%$ to 100%.

Number (%) of subjects considered treatment responders categories, defined as those with a \leq 0%, \geq 0% to < 25%, \geq 25% to < 50%, \geq 50% to < 75%, and \geq 75% to 100% reduction from baseline in seizure frequency during the DB phase will be summarized using descriptive statistics (in both a table and a figure). The analysis will be conducted for primary endpoint seuzures and all seizures, respectively.

Percent change in 28-day frequency of all seizures.

This analysis is similar to primary efficacy endpoint during the DB phase, except all seizure types will be applied.

Change from baseline in the percentage of seizure-free days, based on all seizure types.

The percentages of seizure-free days will be based on all seizure types. Post-baseline percentage of seizure-free days will be calculated as the number of days in the DB treatment phase with zero seizures divided by the number of days with seizure data in the phase, multiplied by 100. The baseline percentage of seizure-free days will be calculated as the number of days in the 4-week baseline phase with zero seizures divided by the number of days with seizure data in the baseline phase, multiplied by 100.

[figure not shown]
The baseline and post-baseline values and the arithmetic changes from baseline will be summarized using descriptive statistics.

[figure not shown]
Change from baseline in the longest seizure-free interval, based on primary endpoint seizure type and all seizure types.

The longest seizure-free intervals (percentage of days) will be based on both the primary seizure types and all seizure types. The post-baseline longest period of time seizure-free is defined as the longest seizure-free period (days) in the DB treatment phase divided by the days with seizure data during the phase, and then multiplied by 100%. The baseline longest period of time seizure-free is defined as the longest individual seizure-free period (days) in the baseline phase divided by the days with seizure data during the baseline phase, and then multiplied by 100%. For both phases, the longest period is based on the number of days without an interruption of a day with a seizure. If there is an interruption of a day without any seizure data, then that day will not count. For example, if there are seizures on January 1st, no seizures on January 2nd through 4th, no seizure data on January 5th, no seizures on January 6th, and there are seizures on January 7th, then the longest period of time seizure free in this interval would be 4 days (January 2nd through 4th and January 6th).

The longest seizure-free interval will be summarized using descriptive statistics for the baseline and post-baseline values, as well as the arithmetic changes from baseline.

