- k. Concomitant ASMs or their dose must be stable for 4 weeks prior to screening and should not be changed at any time prior to Visit 12. Concomitant ASM levels at Visit 1 (Screening), Visit 8, and on study completion will be obtained centrally for the following if the participant is prescribed these medications: cannabidiol, clobazam (which requires clobazam and desmethylclobazam levels), any mTOR inhibitor (including everolimus, sirolimus, etc.), and/or valproate.
- l. If the levels of any ASM co-administered with the IP are measured routinely per standard of care, this information will be recorded in the eCRF.
- m. Only for participants \geq 11 years of age, if appropriate, otherwise, clinical judgment will be used.
- n. For participants aged 4 to 12 years of age, if appropriate ([Section 8.2.5](#)).
- o. For participants \geq 13 years of age, if appropriate.
- p. For parent(s)/caregiver(s)/LAR(s) of the participant to complete, if appropriate. Peds-QL-FIM for past 1 month at baseline visit and Peds-QL-FIM for past 7 days at on-study visits (see [Section 8.2.7](#)).

Table 1 Schedule of Assessments Continued - Part B for Participants who Continue in the OLE^a

Part B (For Participants who Continue in the OLE)						
	Last Visit in Period	Double-blind Phase (Titration) (4 Weeks)			End of Study Visit/ET /First Visit of the OLE	
WEEK (All dates are relative to the first dose)	Wk 16	Wk 16(3 Days Post-V12)	Wk 17	Wk 18	Wk 19	Wk 20
Visit and Visit Window (visits are either in person or telehealth)	± 3 days	± 1 day	All windows for these visits are ± 3 days			± 3 days
VISIT	V12	V13B Phone	V14 Phone	V15	V16 Phone	V17
Screening and Diagnosis						
Informed Consent for OLE entry ^b						X
Inclusion/Exclusion Criteria for OLE	X					X
Safety Assessments						
Vital signs (BP, HR, and RR), Body temperature, Height, and Weight	X			X		X
Physical/Neurological/ Developmental Exam Follow-up	X					X
12-Lead ECG	X			X		X
Clinical Laboratory Tests ^c	X					X
Urinalysis	X					X
Drug Screen						X
Pregnancy Test (WOCBP) ^d	X					X
Tanner Staging						X
Investigational Product PK ^e	X			X		X

Part B (For Participants who Continue in the OLE)						
	Last Visit in Period	Double-blind Phase (Titration) (4 Weeks)			End of Study Visit/ET /First Visit of the OLE	
WEEK (All dates are relative to the first dose)	Wk 16	Wk 16(3 Days Post-V12)	Wk 17	Wk 18	Wk 19	Wk 20

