8.2.6 Anxiety, Depression, and Mood Scale

The ADAMS is a rating scale designed to screen for anxiety and depression in individuals with intellectual disability (Esbensen et al, 2003). The 28-question scale is filled out by the parent(s)/caregiver(s)/LAR(s) and is based on the participant's behavior. Each question will be rated on 4-point Likert scale as follows: 0- behavior has not occurred or is not a problem; 1- behavior occurs occasionally or is a mild problem; 2- behavior occurs quite often or is a moderate problem; and 3- behavior occurs a lot or is a severe problem (see [Section 10.13](#)).

The ADAMS will be conducted at Visit 2 (baseline), Visit 4 (Week 1), Visit 8 (Week 5), Visit 9 (Week 9), and Visit 12 (Week 16).

Participants who continue in the OLE will also have the ADAMS conducted at Visit 15 (Week 18) and Visit 17 (Week 20).

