8.2.7 Pediatric Quality of Life Inventory - Family Impact Module

Peds-QL-FIM is designed to measure the impact of pediatric chronic health conditions on parents and the family. The Peds-QL-FIM measures parent self-reported physical, emotional, social, and cognitive functioning, communication, and worry. The module also measures parent-reported family daily activities and family relationships (see [Section 10.14](#)).

The Peds-QL-FIM will be conducted at Visit 2 (baseline), Visit 8 (Week 5), Visit 9 (Week 9), and Visit 12 (Week 16). Peds-QL-FIM for past 1 month will be conducted at baseline visit and Peds-QL-FIM for past 7 days will be conducted at on-study visits (see [Section 10.14](#)).

Participants who continue in the OLE will also have the Peds-QL-FIM conducted at Visit 15 (Week 18) and Visit 17 (Week 20).

8.2.8 Short Form 36

The SF-36 is a multi-purpose survey designed to capture participant or parent(s)/caregiver(s)/LAR(s) perceptions of own health and well-being. The SF-36 has 36 items grouped in 8 dimensions: physical functioning, physical and emotional limitations, social functioning, bodily pain, general, and mental health. Version 2 of SF-36 will be used for this study (see [Section 10.15](#)).

The SF-36 will be conducted at Visit 2 (baseline), Visit 4 (Week 1), Visit 8 (Week 5), Visit 9 (Week 9), and Visit 12 (Week 16).

Participants who continue in the OLE will also have the SF-36 conducted at Visit 15 (Week 18) and Visit 17 (Week 20).

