10.13 Appendix 13: Anxiety, Depression, and Mood Scale (ADAMS)

Anxiety, Depression, and Mood Scale (ADAMS) - Baseline

Instructions

The Anxiety, Depression and Mood Scale (ADAMS) contains a list of behaviors that can be found among individuals with intellectual disability. Please describe the individual's behavior over the last 6 months

- 0 behavior has not occurred, or is not a problem.
- 1 behavior occurs occasionally, or is a mild problem.
- 2 Behavior occurs quite often, or is a moderate problem.
- 3 behavior occurs a lot, or is a severe problem.

		not a problem	mild problem	moderate problem	severe problem
1.	Nervous	0	1	2	3
2.	Problems initiating communication	0	1	2	3
3.	Does not relax or settle down	0	1	2	3
4.	Has periods of over-activity	0	1	2	3
5.	Sleeps more than normal	0	1	2	3
6.	Withdraws from other people	0	1	2	3
7.	Tense	0	1	2	3
8.	Engages in ritualistic behaviors	0	1	2	3
9.	Depressed mood	0	1	2	3
10.	Sad	0	1	2	3
11.	Worried	0	1	2	3
12.	Has developed difficulty staying on task or completing work	0	1	2	3
13.	Shy	0	1	2	3
14.	Easily fatigued (not due to being overweight)	0	1	2	3
15.	Anxious	0	1	2	3
16.	Repeatedly checks items	0	1	2	3
17.	Easily distracted	0	1	2	3
18.	Lacks energy	0	1	2	3
19.	Avoids others, spends much of time alone	0	1	2	3
20.	Easily upset if ritualistic behaviors are interrupted	0	1	2	3
21.	Lacks emotional facial expressions	0	1	2	3
22.	Has shown difficulty in starting routine tasks	0	1	2	3
23.	Listless	0	1	2	3
24.	Experiences panic attacks	0	1	2	3
25.	Avoids eye contact	0	1	2	3
26.	Trembles when frightening situations are not present	0	1	2	3
27.	Avoids peers	0	1	2	3
28.	Tearful	0	1	2	3

Anxiety, Depression, and Mood Scale (ADAMS) – Post-baseline Visits

Instructions

The Anxiety, Depression and Mood Scale (ADAMS) contains a list of behaviors that can be found among individuals with intellectual disability. Please describe the individual's behavior since the last visit (post-baseline visits).

- 0 behavior has not occurred, or is not a problem.
- 1 behavior occurs occasionally, or is a mild problem.
- 2 behavior occurs quite often, or is a moderate problem.
- 3 behavior occurs a lot, or is a severe problem.

		not a problem	mild problem	moderate problem	severe problem
1.	Nervous	0	1	2	3
2.	Problems initiating communication	0	1	2	3
3.	Does not relax or settle down	0	1	2	3
4.	Has periods of over-activity	0	1	2	3
5.	Sleeps more than normal	0	1	2	3
6.	Withdraws from other people	0	1	2	3
7.	Tense	0	1	2	3

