2.3.2. Key Secondary Efficacy Endpoints

- Percentage change from baseline in 28-day primary endpoint seizure frequency during the maintenance period.
- Number (%) of participants considered treatment responders during the double-blind phase.
- Number (%) of participants considered treatment responders during the maintenance period.
- CGI-I at the last scheduled visit in the double-blind phase.

2.3.3. Secondary Efficacy Endpoints (Behavior/Neuropsychiatric/Quality of life):

- Change from baseline in ADAMS total score and sub-score.
- Change from baseline in quality-of-life scales: Peds-QL-FIM, SF-36, and ELDQOL.

2.3.4. Secondary Efficacy Endpoints (Seizure Control):

- Change from baseline in the percentage of seizure-free days during the double-blind phase, based on primary endpoint seizure type.
- Change from baseline in the percentage of seizure-free days during the maintenance phase, based on primary endpoint seizure type.
- CGI-CSID at the last scheduled visit in the double-blind phase.
- Participants with a $\geq 25\%$ and $\geq 75\%$ reduction from baseline in primary endpoint seizure frequency during the double-blind phase.

- Participants with a $\geq 25\%$, $\geq 50\%$, and $\geq 75\%$ reduction from baseline in primary endpoint seizure frequency during the maintenance period.
- Responder analysis for primary endpoint seizures and all seizures during the double-blind phase using the following response categories: $\leq 0\%$, $\geq 0\%$ to < 25%, $\geq 25\%$ to < 50%, $\geq 50\%$ to < 75%, and $\geq 75\%$ to 100%.
- Percent change in 28-day frequency of all seizures.
- Change from baseline in the percentage of seizure-free days, based on all seizure types.
- Change from baseline in the longest seizure-free interval, based on primary endpoint seizure types and all seizure types.

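### ADAMS and Peds-QL-FIM changes from baseline span different recall windows, so within-arm changes can mix true change with a change of window; the randomised comparison is not biased

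*SAP*

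**What the plan says.** **ADAMS.** SAP 4.3.5 describes the rating as covering behaviour "during the past 6 months at the Baseline visit and since the last visit at the subsequent visits". The forms in Protocol Appendix 13 agree: the baseline form reads "Please describe the individual's behavior over the last 6 months", and the post-baseline form asks about the interval since the previous visit. Protocol 8.2.6 schedules the scale at baseline and Weeks 1, 5, 9 and 16.

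**Peds-QL-FIM.** The windows are in the protocol, not in SAP 4.3.5. Protocol 8.2.7 states: "Peds-QL-FIM for past 1 month will be conducted at baseline visit and Peds-QL-FIM for past 7 days will be conducted at on-study visits". The Schedule of Activities footnotes repeat this, and Appendix 14 prints both forms.

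**Endpoint and analysis.** SAP 2.3.3 lists "Change from baseline in ADAMS total score and sub-score" and the corresponding change for the quality-of-life scales. SAP 4.3.5 summarises these scales with "descriptive statistics of the baseline and post-baseline values and the arithmetic changes from baseline". The opening of 4.3.5 also promises confidence intervals for treatment differences and some testing, but no model or test is then set out for these scales. Under SAP 3.3 they sit outside the gatekeeping sequence, at an unadjusted two-sided 5%.

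The available text gives no recall-matched baseline, rationale or caveat. SF-36 and ELDQOL each appear as a single form, asking mainly about four weeks, so they do not share the mismatch.

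**The concern.** Subtracting baseline from follow-up treats the two as the same measurement taken twice. Here the questionnaire covers a different length of time on each occasion. The response options depend at least in part on whether a problem occurred: the lowest ADAMS option includes a behaviour that has not occurred, and Peds-QL-FIM runs from never to almost always. A family may find the lowest option easier to choose for a week than for a month. A participant whose state has not changed could then appear to improve.

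For ADAMS the on-study window also varies from visit to visit, so the within-arm trend over time mixes window length with time on treatment. What is at stake is the reading of the within-arm columns: a drop in both arms could be reported as improvement in mood, behaviour or family impact.

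**Working it through.** **1. Window lengths.** The plan gives no figure of its own to reproduce here. Inputs are the ADAMS baseline window of 6 months (about 26 weeks), the visit weeks in Protocol 8.2.6, and the phone visits in the Schedule of Activities (Day 4 and Weeks 2, 3, 4, 11 and 13). The documents do not say whether the previous visit means the last in-person visit or any contact, so both are shown.

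| ADAMS at | In-person: window (weeks) | 26 / window | Any contact: window (weeks) | 26 / window |
|---|---|---|---|---|
| Week 1 | 1 | 26 | 3/7 = 0.43 | 61 |
| Week 5 | 4 | 6.5 | 1 | 26 |
| Week 9 | 4 | 6.5 | 4 | 6.5 |
| Week 16 | 7 | 3.7 | 3 | 8.7 |

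For Peds-QL-FIM, one month against seven days is 28/7 = 4.0 to 30/7 = 4.3.

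**2. Does the window move the score?** The documents cannot settle this. An illustrative simulation (1000 runs, 64 per arm) used a 0-3 item, a stable person-level component with SD 1, independent weekly fluctuation with SD 1, and no true change. All of these are assumptions. Control-arm mean change:

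| Windows, baseline vs on study (weeks) | Rater reports worst week | Rater averages the window |
|---|---|---|
| 26 vs 7 | -0.40 | +0.01 |
| 26 vs 3 | -0.80 | +0.03 |
| 26 vs 1 | -1.41 | +0.08 |
| 4 vs 1 | -0.76 | +0.05 |
| 4 vs 4, or 7 vs 7 | 0.00 | 0.00 |

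The artefact runs from near zero to large depending on how raters use the window, which the documents do not say.

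**3. The randomised comparison.** Baseline is rated before treatment on the same form in both arms, so its expected mean is equal across arms. The on-study form is also the same in both arms. In expectation, the difference in change therefore equals the difference in on-study score, and the recall shift drops out. In the same simulations under no treatment effect, the between-arm difference stayed within 0.005 of zero and the rank-sum test rejected in 4.2% to 6.3% of runs, consistent with 5% given simulation error.

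**4. Precision.** Let the follow-up SD be 1, the baseline SD be k, and their correlation be rho.

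- Change-score variance: 1 + k^2 - 2 rho k.
- ANCOVA variance in large samples: 1 - rho^2.
- Difference: (k - rho)^2, which is never negative.

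With k = 1 the saving is (1 - rho)/2:

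- rho 0.5: 1.00 against 0.75, a saving of 25%.
- rho 0.3: 1.40 against 0.91, a saving of 0.49/1.40 = 35%.

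With unequal SDs at rho 0.5:

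- k = 0.7: 1 + 0.49 - 0.70 = 0.79 against 0.75, a saving of 0.04/0.79 = 5%.
- k = 1.3: 1 + 1.69 - 1.30 = 1.39 against 0.75, a saving of 0.64/1.39 = 46%.

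The values of rho and k are assumptions; the documents give neither.

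**The case against.** The case for leaving the plan alone has real weight.

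- **The scales are not pure frequency counts.** ADAMS options combine occurrence with severity, and the SAP labels them from not a problem to severe. Peds-QL-FIM asks for relative frequency. Neither score has to move when the window shortens. This stands: a recall shift is plausible, not demonstrated.
- **The objective is comparative.** SAP 2.2.2 frames the secondary objectives as GNX against placebo, and the randomised contrast answers that. This stands too. A reader might infer a biased treatment effect, inflated type I error, or an unanswered secondary objective; step 3 shows otherwise.
- **Post-baseline values are tabulated as well.** The arms can already be compared without using baseline. At rho 0.3 that comparison has variance 1.00 against 0.91 for ANCOVA, a gap of 9%. This is true, but the plan defines the endpoint as change and does not say which quantity its promised confidence intervals use.
- **The Peds-QL-FIM windows were chosen deliberately.** The amendment history shows they were specified on purpose. That makes them a decision rather than a slip, but the subtraction still runs across two windows.

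A reader might also want the baseline forms changed to match. The documents do not support doing so mid-trial. It would mix two baseline versions in one variable, there is no single on-study ADAMS window to match, and enrolment status is not given (the SAP was approved in August 2024).

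**Conclusion.** The point holds, as a minor one. All four recall windows and the subtraction across them are confirmed in current text. Within-arm ADAMS and Peds-QL-FIM changes can mix true change with a change of recall window, by an amount the documents do not allow to be estimated. It would go too far to call those changes uninterpretable: if raters average over the window, the shift in the illustration is at most 0.08 on a 0-3 item.

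The between-arm difference is not biased, given randomisation and the same forms in both arms. These endpoints lie outside the gatekeeping, so no primary or key secondary conclusion changes.

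ANCOVA is worth having because it uses baseline only as a predictor, so the two windows need not match, and in large samples it is never less precise than the change score. A reader might take the 25% or 35% saving as the cost of the recall mismatch. It is not: the same formula applies with matched windows, and at rho 0.5 the saving ranges from about 5% to 46% over SD ratios of 0.7 to 1.3.

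**What to change.** In SAP 4.3.5, for ADAMS and Peds-QL-FIM:

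1. Estimate the GNX-placebo difference and its 95% CI by ANCOVA of the post-baseline score on treatment, baseline score and CBD stratum, in place of a comparison of arithmetic changes.
2. Footnote the within-arm changes as not comparable across recall windows. State the windows, including whether the previous visit for ADAMS means in-person or any contact.

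Leave the baseline forms as they are. The cost is SAP and table-shell wording plus a standard model. Baseline scores and the stratification factor are already collected, and ANCOVA already appears in the SAP's abbreviation list, though no analysis in the available text uses it. Naming the model also fills the gap in 4.3.5, which promises confidence intervals for these scales without a method.
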